8.2 ADVERSE EVENTS AND SERIOUS ADVERSE EVENTS

8.2.1 DEFINITION OF ADVERSE EVENTS (AE)

Any untoward or unfavorable medical occurrence in a human subject, including any abnormal sign (for example, abnormal physical exam or laboratory finding), symptom, or disease, temporally associated with the subject's participation in the research, whether or not considered related to the subject's participation in the research. Adverse events encompass both physical and psychological harms.

8.2.2 DEFINITION OF SERIOUS ADVERSE EVENTS (SAE)

An adverse event is serious when the outcome for the subject is:

- Death;
- Life- threatening (place the subject at immediate risk of death from the event as it occurred);
- Inpatient hospitalization or prolongation of existing hospitalization;
- Persistent or significant disability/incapacity;
- congenital anomaly/birth defect; or

when the event does not fit the other outcomes but, based upon appropriate medical judgement, may jeopardize the subject's health and may require medical or surgical intervention to prevent one of the other outcomes.

8.2.3 CLASSIFICATION OF AN ADVERSE EVENT

There will be no classification of adverse events for this minimal-risk study.

8.2.3.1 SEVERITY OF EVENT

The severity of all AEs will be characterized as "mild, moderate, or severe" according to the following definitions:

Mild	An event that does not have an impact on the patient
Moderate	An event that causes the patient some minor inconvenience
Severe	An event that causes substantial disruption to the patient's well-being.
Potentially Life-Threatening	An event that places the subject at immediate risk of death
Death	An event resulting in death

8.2.3.2 RELATIONSHIP TO STUDY INTERVENTION

All AE's will be categorized according to the likelihood that they are related to the study intervention, using the following terms:

- Unrelated to study intervention
- Possibly related to study intervention
- Probably related to study intervention

or

- Definitely related to study intervention

8.2.3 EXPECTEDNESS

Due to the severity of illness present in the study population, unrelated, adverse events are expected to happen during this study that result in worsening of existing medical conditions, hospitalizations, life-threatening events and/or death. All adverse events will be documented and reported to the DSM and reported on a yearly basis.

8.2.4 TIME PERIOD AND FREQUENCY FOR EVENT ASSESSMENT AND FOLLOW-UP

Given that no adverse events are expected related to this minimal risk intervention, adverse events will be documented and assessed as they occur and will be followed until resolution.

8.2.5 ADVERSE EVENT REPORTING

Adverse events must be promptly documented and recorded. All adverse events observed or reported must be recorded, regardless of causality and/or clinical significance.

8.2.6 SERIOUS ADVERSE EVENT REPORTING

Unexpected and/or intervention-related serious adverse events will be reported by the principal investigator within 24 hours to the independent monitor. A report will also be sent to the University of North Carolina IRB and the NIH in accordance with requirements.

Anticipated or unrelated serious adverse events will be reported by the principal investigator within one week to the independent monitor. A report will also be sent to the University of North Carolina IRB and the NIH in accordance with requirements on an annual basis.

8.3 UNANTICIPATED PROBLEMS

8.3.1 DEFINITION OF UNANTICIPATED PROBLEMS (UP)

An Unanticipated Problem (UP) is any incident, experience, or outcome that:

- Is unexpected (in terms of nature, severity, or frequency) given (a) the research procedures that are described in the protocol-related documents, such as the IRB -approved research protocol and informed consent document; and (b) the characteristic of the participant population being studied;
- Is related or possibly related to a participant's participation in the research; and
- Is serious or suggests that the research places participants or others at a greater risk of harm (including physical, psychological, economic, or social harm) that was previously known or recognized.

8.3.2 UNANTICIPATED PROBLEM REPORTING

All unanticipated problems must be reported to the IRB within 7 calendar days of the event.

9 STATISTICAL CONSIDERATIONS

9.1 STATISTICAL HYPOTHESES

Specific aims of this research study include:

1. Evaluate the efficacy of Connect-Home to improve SNF patient and caregiver preparedness for care at home.
 - a. Hypothesis 1a: Compared to patients enrolled in control periods, Connect-Home patients will experience greater preparedness for discharge (primary outcome, measured with the CTM-15), assessed 7 days after discharge home
 - b. Hypothesis 1b: Compared to caregivers of patients enrolled in control periods, Connect-Home caregivers will experience greater preparedness for caregiving (primary outcome, measured with the Preparedness for Caregiving Scale), assessed 7 days after discharge home.
2. Evaluate the efficacy of Connect-Home to improve SNF patient and caregiver outcomes after discharge home.
 - a. Hypothesis 2a: Compared to patients enrolled in control periods, Connect-Home patients will experience better quality of life and function (secondary outcomes), and fewer falls requiring medical assistance (exploratory), measured 30 and 60 days after discharge home
 - b. Hypothesis 2b: Compared to caregivers from control periods, Connect-Home caregivers will experience less burden and caregiver distress (secondary outcomes), measured 30 and 60 days after discharge home
3. Evaluate the efficacy of Connect-Home to prevent acute care use up to 60 days after SNF discharge.
 - a. Hypothesis 3a: Compared to patients enrolled in control periods, Connect-Home patients will have fewer days of acute care use (composite of emergency department and hospital use) (secondary outcome) and more hospice enrollment (exploratory), measured 30 and 60 days after discharge home

9.2 SAMPLE SIZE DETERMINATION

Computer simulations were used to calculate statistical power for comparing control (standard discharge procedures) and intervention (Connect-Home) conditions for primary outcomes and selected secondary outcomes. For each scenario, 1000 simulated datasets were generated with outcomes clustered within SNFs for the stepped-wedge design in Figure 2 and the respective linear mixed models (Log CTM-15, Preparedness for Caregiving Scale, MQoL-R, Life Space Assessment, Zarit Caregiver Burden scale) and MZIP random intercept model (Days of acute care use). Based on preliminary data for Aim 1, we assumed that the group difference in log CTM-15 scores was $\theta=0.15$. We also assumed that responses from patients within the same SNF in the same period would have an intra-cluster correlation of 0.10 (ICC_w). We assumed that responses from patients or caregivers in the same site but from different periods would have an intra-cluster correlation of 0.05 (ICC_b); together with the total variance of the outcome (SD^2), these values determine and in the linear mixed models of Aims 1 and 2. Under these assumptions and accounting for 23% dropouts, 277 patients at 7 days post-discharge will provide 89% power to detect an increase of 0.15 in the mean log CTM-15 score (equivalent to a 16% increase in

the mean CTM-15 score) among intervention patients relative to control patients, using a two-sided test at the 5% significance level. Power for Caregiver Preparedness is similarly determined. Power for secondary outcomes at 30 days post-discharge assumes a 30% dropout rate. For the control group in Aim 3, we assumed a prevalence of 22% of patients having at least one day of acute care use and, among those patients, a truncated-at-zero mean of 4.0 days. These assumptions imply that the overall mean number of acute care use days is 0.881 and the excess zero probability is 0.776. For the intervention group, we assumed an overall mean acute care use days of 1.8 and excess zero probability 0.685. Thus, assuming 30% dropout and (optimistically) zero intraclass correlation within SNFs, the MZIP model for independent outcomes has 82% power (not shown); however, the MZIP model with empirical standard errors adjusting for possible clustering within SNFs has 71% power. If there is positive intraclass correlation, power will be lower. However, for days of acute-care use within 60 days of discharge, power is higher than for 30 days due to higher prevalence and mean number of days of acute care use.

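### The acute-care power calculation assumes that Connect-Home doubles days of acute care, whereas Hypothesis 3a predicts a reduction

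*Combined protocol and SAP*

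**What the plan says.** Hypothesis 3a in section 9.1 of the combined protocol and SAP gives the direction: "Connect-Home patients will have fewer days of acute care use" than patients enrolled in control periods.

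Section 9.2 builds the control assumption for 30 days from two inputs. The first is the share of users: "we assumed a prevalence of 22% of patients having at least one day of acute care use". The second is the length of use: "among those patients, a truncated-at-zero mean of 4.0 days". It continues: "These assumptions imply that the overall mean number of acute care use days is 0.881 and the excess zero probability is 0.776". For the other arm it says: "For the intervention group, we assumed an overall mean acute care use days of 1.8 and excess zero probability 0.685".

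The power follows directly from these values: "assuming 30% dropout and (optimistically) zero intraclass correlation within SNFs, the MZIP model for independent outcomes has 82% power (not shown"), and "the MZIP model with empirical standard errors adjusting for possible clustering within SNFs has 71% power". Section 9.2 adds that positive intraclass correlation would lower power, and that power at 60 days is higher, without giving a figure. Nothing in the section says that the arms are reversed, and no intervention mean below 0.881 is given.

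**The concern.** The assumed intervention mean is about twice the control mean. Both intervention parameters point the same way: a higher mean and a smaller share of excess zeros. The calculation therefore gives the chance of detecting an increase in acute-care days.

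The two-sided test does not make this harmless. For counts with many zeros, the precision of a log rate ratio depends on how many events each arm yields. Doubling the control mean adds events, and halving it removes them, so the same ratio in the opposite direction has less power when the control rate is fixed.

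These are the only numerical power figures in the plan for days of acute care use. If Aim 3 gives a null result, readers will take 71% to 82% as the chance the trial had of detecting a benefit.

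**Working it through.** **Inputs.** Sections 1.1 and 9.2: 360 patients and 30% dropout, so 360 × 0.70 = 252. Allocation in Figure 2 is close to 1:1, taken here as 126 per arm. Section 9.4.1: two-sided 0.05. Section 9.4.3: marginalized zero-inflated Poisson (MZIP) model, with the IRR of overall means as the effect measure. Section 9.2: zero intraclass correlation. Our assumption: no time term, because section 9.2 does not say whether the simulation had one.

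**Step 1: control arm.** Let λ be the Poisson mean and ψ the excess-zero probability.
- λ/(1 − e^−λ) = 4.0 gives λ = 3.921.
- ψ = 1 − 0.22/(1 − e^−3.921) = 0.776.
- Overall mean = 0.22 × 4.0 = 0.880.

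These match the plan's 0.776 and 0.881 within rounding, so 0.881 is tied to the control inputs.

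**Step 2: intervention arm.**
- λ = 1.8/(1 − 0.685) = 5.714.
- Any use = 0.315 × (1 − e^−5.714) = 31.4%, against 22% in control.
- Days per user = 1.8/0.314 = 5.73, against 4.0 in control.
- IRR = 1.8/0.881 = 2.04, or 0.919 more days per patient.

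**Step 3: the plan's own power.** Per arm, Var(log mean) = (1 + ψλ)/(nμ), with λ = μ/(1 − ψ).
- Control: λ = 0.881/0.224 = 3.933; (1 + 0.776 × 3.933)/(126 × 0.881) = 0.0365.
- Intervention: (1 + 0.685 × 5.714)/(126 × 1.8) = 0.0217.
- SE = √(0.0365 + 0.0217) = 0.241; z = ln(2.043)/0.241 = 2.96; power = Φ(2.96 − 1.96) = 84%.

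MZIP maximum-likelihood simulations on the Figure 2 layout gave 84% to 86% with model-based standard errors. With SNF-clustered empirical standard errors and a t reference on 5 df they gave 72% to 73%. The plan states 82% and 71%. The Monte Carlo margin of 1000 replicates at 82% is about ±2.4 points, so the printed contrast accounts for the stated power. In one set of 1000 simulated trials, 99.8% of the estimates showed more acute-care days under Connect-Home.

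**Step 4: a reduction from the stated control rate.** The plan gives no target, so we take the mirror image as an illustration: IRR 1/2.04 = 0.49, mean 0.881 × 0.49 = 0.43 days.
- Fewer users (λ held at 3.933, ψ = 0.890): intervention variance 0.0829; SE = √(0.0365 + 0.0829) = 0.345; z = 2.07; power 54%.
- Shorter use (ψ held at 0.776, λ = 1.925): intervention variance 0.0459; SE = 0.287; z = 2.49; power 70%.

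Simulated model-based power was about 56% and 69% to 71%. With empirical standard errors on t(5) it was about 46% to 47% and 60%.

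Other reductions, same formula:

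| IRR | Fewer users | Shorter use |
|---|---|---|
| 0.8 | 12% | 13% |
| 0.7 | 22% | 25% |
| 0.6 | 36% | 44% |
| 0.4 | 69% | 88% |

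**Step 5: can a slip explain it?**
- Decimal slip (0.18 for 1.8, with ψ = 0.685): power above 99%, which does not fit 82%.
- Swapped arms (control 1.8, intervention 0.881): the two variance terms change places, so power stays at 84% by formula, and simulation gave about 85% and 74%. The control arm would then have 31.4% users at 5.7 days, not the 22% and 4.0 days stated.

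**The case against.** The strongest reply is that the arm labels were swapped. With equal arms the power is then unchanged, and 82%/71% would apply to a genuine reduction from 1.8 to 0.881. The near match in Step 3 cannot tell the two readings apart. This stands as a possible explanation. It does not rescue the paragraph, because 0.881 is explicitly derived from the control inputs. Under a swap those inputs are wrong, and the trial would be counting on a control rate about twice the one it states.

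A second point is that the match rests on choices the plan does not report. With a linear trend in the mean part, the model-based figure for the printed contrast is 74.5%. With a normal reference, the empirical-SE figure is about 87%. That is correct, and we do not claim that 82% was miscalculated. Neither choice alters the direction of the assumed effect.

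Third, the reductions in Step 4 are our scenarios and not the trial's. That is also correct; they show the range and do not measure the trial's true power.

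Finally, the endpoint is secondary. The primary CTM-15 calculation, the enrolment target and the planned analysis are unaffected, and the plan already calls zero intraclass correlation optimistic. This limits the consequences but does not remove the contradiction.

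**Conclusion.** The concern holds. As written, section 9.2 powers the acute-care endpoint for an IRR of 2.04 against Connect-Home, while Hypothesis 3a predicts an IRR below 1. The contradiction needs no modelling assumption.

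Its size depends on the repair. If the control assumption of 0.881 days is right, power for the mirror-image reduction is about 54% to 70% model-based and about 46% to 60% with the planned empirical standard errors, against the stated 82% and 71%. Smaller reductions have much less. These figures assume 252 patients split equally, zero intraclass correlation and no time term; section 9.2 itself says positive correlation would lower power. If the labels were swapped, the power figures broadly stand, but the control assumption of 22% users and 4.0 days does not. The documents do not settle which reading is right, and on neither can the paragraph stand.

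**What to change.** Confirm from the original simulation inputs which arm each set of values belongs to.

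- If control is 0.881 days, choose and justify an intervention mean below it. State whether the reduction comes from fewer users, shorter use or both, re-run the simulation, and replace 82% and 71% with the results.
- If the labels were swapped, restate the control assumption as a mean of 1.8 days with excess-zero probability 0.685 (31.4% users, 5.7 days per user), justify it, and correct the intervention values to match.

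In both cases give the detectable IRR, the reference distribution used with the empirical standard errors, and whether the simulated model had a time term. The cost is one simulation run and one rewritten paragraph. Enrolment and the planned analysis need not change, though the stated power will probably be less favourable.

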9.3 POPULATIONS FOR ANALYSES

An intent to treat analysis will be used in which all patients/caregivers are included in the analysis according to their treatment allocation at enrollment, regardless of whether they receive the full intervention.

9.4 STATISTICAL ANALYSES

9.4.1 GENERAL APPROACH

Descriptive statistics will be used for all variables. If patients or caregivers with missing covariates are few (< 5%), unconditional mean imputations will be used to impute missing values for continuous covariates and unconditional mode imputation for categorical covariates. If 5%-15% of patients or caregivers have missing covariates, conditional mean imputation will be used. If missing covariate data exceed 15%, multiple imputation will be used. Missing outcomes will not be imputed. For continuous variables that are highly skewed, the statistical team will log-transform the data for analysis. All statistical tests will be two-tailed with 0.05 significance levels. Also, descriptive statistics will be used to describe intervention fidelity (receipt, delivery and enactment). Finally, in the absence of strong temporal effects, balance in covariates is expected between control and intervention patients; supplemental analyses will involve assessing the impact of the covariates (i.e., insurance provider, SNF length of stay, race, gender, and others determined with bivariate analyses) on outcomes in the statistical models for aims 1-3.

Finally, to determine the extent the intervention effect can be attributed to home health care use, a general multilevel approach will be used to causal mediation analysis to evaluate home health care use as a mediator for intervention effect on outcomes as a secondary analysis. This approach uses two

random effects models within the counterfactual framework: 1) for the mediator (number of days of home health care use) as a function of treatment condition and covariates and 2) for the outcome as a function of treatment condition, mediator, and covariates. Outputs include indirect and direct effects of the intervention.

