4.2 SCIENTIFIC RATIONALE FOR STUDY DESIGN

The study will utilize a SW-CRT, as it retains statistical power to evaluate efficacy of the intervention on the primary outcome in a relatively small number of SNFs. Observing SNF's under standard practice followed by the Connect-Home intervention is also consistent with the actual practice of implementing organizational change in SNFs and provides opportunities for evaluating implementation procedures. Cluster randomization at the nursing home level reduces risk of contamination between control and Connect-Home participants (Figure 2).

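### Two primary outcomes are each tested at two-sided 0.05, with no multiplicity rule and no statement of whether one or both must succeed

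*Combined protocol and SAP*

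**What the plan says.** The synopsis (1.1) and the objectives table (3) list CTM-15 and PCS, both at seven days, as primary endpoints 1.1 and 1.2. Section 9.1 places both under Aim 1 and labels each one primary:

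- Hypothesis 1a: "Connect-Home patients will experience greater preparedness for discharge (primary outcome, measured with the CTM-15"
- Hypothesis 1b: "Connect-Home caregivers will experience greater preparedness for caregiving (primary outcome, measured with the Preparedness for Caregiving Scale"

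Section 9.4.1 fixes the level for every test: "All statistical tests will be two-tailed with 0.05 significance levels". The CTM-15 power statement in 9.2 uses the full level, "using a two-sided test at the 5% significance level", and reports that "277 patients at 7 days post-discharge will provide 89% power to detect an increase of 0.15 in the mean log CTM-15 score". For PCS, 9.2 says only that power was obtained in a similar way and gives no figure.

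Section 9.4.2 describes one model per outcome and a 95% confidence interval for the CTM-15 group difference. It gives no alpha split, testing order, step-wise procedure or success rule. Section 4.2 uses the singular when it says that the design can "evaluate efficacy of the intervention on the primary outcome in a relatively small number of SNFs", without saying which outcome is meant.

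**The concern.** The two outcomes serve one aim, come from the same enrolled dyads in the same six SNFs, and test one intervention. Under the rule as written, a p-value between 0.025 and 0.05 on one outcome, with nothing on the other, could be reported as success on a primary outcome. Nothing in the plan prevents this, and nothing limits how often it would happen by chance. Because the success rule is open, it could also be settled after the results are known. At stake is whether a confirmatory claim that rests on one of the two outcomes has a stated error rate.

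**Working it through.** **Inputs from the documents**
- Level: two-sided 0.05 per test (9.4.1; 9.2 for CTM-15).
- CTM-15 power: 89% with 277 evaluable patients (9.2).
- Enrolment of 360 patients and 23% dropout at seven days (4.1, 9.2).

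**Inputs the documents do not give (assumed, with ranges)**
- Correlation ρ between the two test statistics: 0 to 0.7. A positive value is plausible, because a representative or caregiver answers the CTM-15 for some patients (8.1, 9.4.2).
- PCS power: 89%, 80%, 70%, 60%, or no effect.
- Each mixed-model test holds its nominal level with six SNFs.

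**The plan's own figures.** 360 × 0.77 = 277.2, so 277 reproduces. exp(0.15) = 1.162, so the 16% increase reproduces. The 89% cannot be checked, because no SD for log CTM-15 is given; it is taken as stated.

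**Error with no rule, neither effect real, ρ = 0**
- At least one two-sided rejection: 1 − 0.95² = 9.75%.
- At least one false finding of benefit: 1 − 0.975² = 4.94%, against 2.5% for a single test.

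**Error under Hochberg, ρ = 0.** Both outcomes are significant if both p ≤ 0.05; otherwise the smaller p must be ≤ 0.025. The chance of any rejection is (1 − 0.975²) + 0.025² = 4.94% + 0.06% = 5.00%.

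For ρ > 0, the same events are evaluated with the bivariate normal distribution:

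| ρ | Any rejection, no rule | Any false benefit, no rule | Any rejection, Hochberg |
|---|---|---|---|
| 0 | 9.8% | 4.9% | 5.0% |
| 0.3 | 9.5% | 4.8% | 4.9% |
| 0.5 | 9.1% | 4.5% | 4.8% |
| 0.7 | 8.3% | 4.2% | 4.6% |

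The first column falls below 9% once ρ exceeds about 0.53.

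**Power cost for CTM-15.** Power of 89% corresponds to a non-centrality of 1.960 + 1.227 = 3.187. At two-sided 0.025 (critical value 2.241), power is Φ(3.187 − 2.241) = 82.8%. With ρ = 0, CTM-15 wins under Hochberg if its own p ≤ 0.025, or if its p lies between 0.025 and 0.05 and PCS also has p ≤ 0.05:

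- PCS power 89%: 82.8% + (89.0% − 82.8%) × 0.89 = 88.3%, a loss of 0.7 points.
- PCS without effect: 82.8% + (89.0% − 82.8%) × 0.05 = 83.1%, a loss of 5.9 points.

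Over the full range of ρ:

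| Assumed PCS power | CTM-15 power, ρ = 0 | CTM-15 power, ρ = 0.7 | Loss from 89% (points) |
|---|---|---|---|
| 89% | 88.3% | 87.4% | 0.7-1.6 |
| 80% | 87.7% | 86.2% | 1.3-2.8 |
| 70% | 87.1% | 85.1% | 1.9-3.9 |
| 60% | 86.5% | 84.3% | 2.5-4.7 |
| No effect | 83.1% | 83.1% | about 5.9 |

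**Other power measures, both outcomes at 89%.** Power for at least one win falls from 98.8% to 97.4% at ρ = 0 and from 96.3% to 93.6% at ρ = 0.5. Power to win on both is the same with or without Hochberg: 0.89² = 79.2% at ρ = 0, rising to 83.3% at ρ = 0.7.

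**The case against.** The plan states separate objectives and hypotheses for patients and for caregivers. If each is reported only on its own terms, each keeps its 5% error. Aim 1 names patient and caregiver preparedness together; if that means both must improve, there is no inflation. This stands in part: the either-one-wins rule is a condition of the calculation and is not written in the plan. But neither is the both-required rule, nor a statement that the two hypotheses will be kept apart.

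A reader might infer that the trial has a 9-10% chance of a false claim of benefit. The documents do not support that. Both hypotheses are directional, and the 9-10% counts rejections in either direction; false benefit claims alone are 4.2-4.9%. That is still 1.7 to 2 times the single-test 2.5%.

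A reader might also infer that the plan doubles an overall 5% that it promised. It promises no overall rate: 9.4.1 and 9.2 give 5% per test.

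Finally, Hochberg is one remedy among several. A fixed testing order or a both-required rule would also settle the question. This is correct, and the choice belongs to the sponsor.

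**Conclusion.** The gap is real: two primary outcomes, full alpha on each, and no rule for combining them. Its size is conditional. The figure of about 9-10% requires that a win on either outcome counts, that neither effect is real, and that the correlation is no more than about 0.5; at 0.7 it is about 8.3%. All the error rates rest on each mixed-model test holding its nominal level with six SNFs.

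It would be tempting to say that the remedy costs about one power point whenever both effects are real. The documents do not support this, because it needs PCS power near 89% and section 9.2 gives no PCS figure.

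The analysis is not invalid as it stands. The plan should be changed, because the remedy is standard and needs no new data, larger sample or change to the models.

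**What to change.** Before outcome data are examined, add to 9.4.2: CTM-15 and PCS are tested by the Hochberg procedure at overall two-sided 0.05; both are significant if both p ≤ 0.05, and otherwise the one with the smaller p-value is significant only if that value is ≤ 0.025.

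If the sponsor intends both outcomes to be required for success, state that instead. No alpha adjustment is then needed, but the relevant power is the joint power: about 79-83% for ρ from 0 to 0.7 if PCS power is also 89%.

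The cost of Hochberg is the CTM-15 power loss tabulated above, which falls only on a lone win with p between 0.025 and 0.05. Two passages need aligning. The power statement in 9.2 should note the loss and give a power figure for PCS. Section 9.4.2 should say that the 95% interval is unadjusted, because it can exclude zero when the outcome is not significant under Hochberg. The singular wording in 4.2 should be made to agree with two primary outcomes.
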